**Research Repositories:** If the purpose of this submission is to establish a Research Repository (bank, registry) indicate whether the material you plan to collect would or would not be available from a commercial supplier, clinical lab, or established IRB approved research repository. Provide scientific justification for establishment of an additional repository collecting duplicate material. Describe the repository design and operating procedures. For relevant information to include, see the [UK Research Biospecimen Bank Guidance](#) or the [UK Research Registry Guidance](#).

This study will use a single-blind, placebo controlled, three-arm, parallel-design. Thirty subjects with moderate to severe Alzheimer's disease as primary dementia type (Clinical Dementia Rating Scale score of 2-3) will be randomly assigned to one of three arms: standard care; standard protocol (pre-determined set of environmental design modifications); or personalized protocol (environmental design modification developed with subject based on sensory preference and behavioral needs). Intervention will last 4 weeks. Weekly monitoring for protocol adherence and adverse events will occur throughout study. An follow-up 4 weeks post-intervention will occur. The entire project will be conducted over 10 weeks of participant engagement.

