**Individualized Environmental Design Protocol:** Participants' caregivers will receive standard recommendations of physical environment modifications and caregiving techniques. Physical environmental modifications will include declutter living space, reduce background noise, increase natural light, accommodate for accessibility to commode and areas for drinking and eating. Caregiving techniques will include training for calming demeanor (emotional contagion), needs-driven care to decrease onset of behavioral disruption, and accepting and accommodating approach to behavioral disruption. Individualized sensory stimulation kits will be developed using subjects' preferred sensory stimuli (as determined by the Adult Sensory Profile assessment) and behavioral concerns identified in the COPM. One target behavior and/or time period of the day will be targeted for improvement. Selection of items included in the individualized sensory kit will be determined based on the attached decision tree and sensory mode plans. The sensory kit will be provided via caregiver administration or supervision two scheduled times (once in the morning and once in the afternoon) per day and one time as needed prior to activity or task associated with behavior concern to promote maintained behavioral regulation and adaptive responses.

**Data Analysis:** Due to the nature of feasibility of this study, sample size of 30 participants with cognitive impairment (10 per arm) does not fully power the study. Statistical description of behavior change results will be explorative and descriptive in nature. Per-protocol analysis (PPA) will be performed with 75% or more adherence to program as determined from weekly visits and journals. Power analyses for secondary outcome measures cannot be performed as this study is a preliminary investigation of these secondary outcome measures.

Summary statistics will be tabulated for the behavior change, protocol adherence, and adverse events. The frequencies of behavior change, protocol adherence, and adverse events will be compared between participants within same group and between group for differences.

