Once eligibility is confirmed, the research assistant will email a REDCap link to the caregiver for the Zarit Caregiver Burden and the Adult Sensory Profile, Actigraph and charger, and a copy of consent forms to the participant's caregiver. The PI will complete the COPM on visit 1, and provide caregiver and participant with Actigraph wear and care instructions. The VABS will be emailed to the caregiver via a confidential link through Pearson Publishing.

Subjects will be randomized to treatment arms by the statistical team. Participants will be randomized into one of the three groups: control, standard environmental design protocol, individualized environmental design protocol. Recruitment will be ongoing until all groups have 10 participants. In the event of drop out or early termination (causes will be recorded), researchers will recruit for replacement participants so that the study is completed with 30 entire study duration cases.

Visit 2 will consist of baseline assessment. A research assistant or the PI will complete the MOCA, with the participant with dementia. The caregiver will complete the NPI. Following Visit 2, an occupational therapist will be provided results of the COPM and ASP for participants of the individualized treatment arm. A sensory protocol will be developed based on assessment results following predetermined guidelines. All intervention materials for all study participants will be mailed to caregivers within 4 days of Visit 2. Upon receipt of intervention supplies, caregivers will contact the PI or occupational therapist for study initiation. Visit 3 will provide caregiver training for intervention use and initiation of Actigraph use. Adverse events since Visit 2 will be recorded. Visit 3 marks day 1 of intervention implementation. Participants will mail Actigraph back to UKADC in provided pre-paid envelop following week one of intervention.

Visits 4-8 will be scheduled at the end of each week following Visit 3. The PI, occupational therapist, or research assistant will record concurrent medication, and adverse events. With the caregiver, the interviewer will review behaviors observed by the caregiver, the behavior journal, compliance and acceptance of the intervention by the caregiver and the person with dementia. Actigraphs will be mailed from UKADC to participants, and patient will be asked to wear actigraph for last week of intervention window.

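### Filling each arm to 10 and replacing drop-outs to 30 full-duration cases, with no stated allocation rule for replacements, makes some late assignments forced and potentially foreseeable

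*Combined protocol and SAP*

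**What the plan says.** The study design text states that 30 subjects "will be randomly assigned to one of three arms". Research Procedures gives the task to the statisticians: "Subjects will be randomized to treatment arms by the statistical team". The same paragraph then sets the stop by arm, "Recruitment will be ongoing until all groups have 10 participants", and adds that after a drop-out or early termination "researchers will recruit for replacement participants so that the study is completed with 30 entire study duration cases". The Data Analysis paragraph gives the intended split: "sample size of 30 participants with cognitive impairment (10 per arm) does not fully power the study".

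The text supplied does not say how a replacement gets its arm, how the sequence is generated or blocked, how assignments are concealed, or what drop-out is expected. The design is called single-blind without naming who is blinded. The Statistical Analysis section does not mention replacements. For secondary and exploratory endpoints it analyses dyads with at least one video session. Research Procedures refers to an attached detailed protocol, which is not part of the documents supplied.

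**The concern.** Randomisation protects the comparison only while the next assignment does not depend on what happened to earlier participants and cannot be foreseen by those who decide who enters. A quota of full-duration cases in each arm weakens both conditions. An arm that has reached its number has to close, and an arm that loses a dyad has to reopen, so drop-out after randomisation steers later assignments. When only one arm is open, the next assignment is certain whoever issues it.

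The staffing makes this relevant. Under Research Procedures:

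- A research assistant or the PI obtains consent and determines eligibility.
- The PI reviews the chart and completes the COPM at Visit 1.
- The PI or a research assistant gives the baseline MoCA.
- The PI, an occupational therapist or a research assistant runs the weekly visits, where use of the intervention is reviewed.

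People in these roles can learn which arm a dyad is in and which dyads have left, and some of them also judge the next candidate. Caregivers deliver the programme, and the primary endpoint in the Statistical Analysis section is completion of at least 75% of video sessions, so caregiver capability bears directly on the result. The covariates named there (baseline value, age of the person with AD, caregiver gender) would not remove selection on capability. With about 10 dyads per arm, two or three selected dyads could matter.

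**Working it through.** **The plan's own figure.** 3 arms x 10 per arm = 30. This reproduces. It is a feasibility number, so there is no power formula to check.

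**Replacements.** With drop-out rate d, assumed equal and independent across arms, reaching 30 completers takes 30/(1-d) dyads on average. Of these, 30d/(1-d) are replacements, which is a share d of the total. At d = 20%: 30/0.8 = 37.5 randomised, 7.5 replacements, 7.5/37.5 = 20%.

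**Forced assignments.** A replacement is not automatically a forced assignment. An assignment is counted as forced when only one arm is still open. Three ways of running the quota were simulated, 20,000 runs per cell:

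- *Re-issue*: randomise 10/10/10 first, then re-issue the vacated places in shuffled order (only replacements can count as forced).
- *Open-arm draw*: draw with equal probability among arms still below 10 completers.
- *Pool*: return a vacated place at once to the pool of remaining places and draw from that.

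| Assumed d | Randomised / replacements | Forced: re-issue | Forced: open-arm draw | Forced: pool |
|---|---|---|---|---|
| 0% | 30.0 / 0 | none | 9.8% | 4.8% |
| 5% | 31.6 / 1.6 | 3.2% | 9.8% | 4.7% |
| 10% | 33.3 / 3.3 | 4.7% | 9.7% | 4.8% |
| 20% | 37.5 / 7.5 | 6.7% | 9.7% | 4.8% |
| 30% | 42.9 / 12.9 | 8.4% | 9.7% | 4.8% |

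For the last two schemes the share hardly moves with d and is already present at d = 0. There the cause is the fixed number per arm, not drop-out. Only a fourth scheme, placing each replacement directly in the vacated arm, gives a forced share equal to d.

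**Partly foreseeable assignments.** With one arm closed and two open, the next assignment is still narrowed. Assignments made with at least one arm closed are about 5-17% of the total under re-issue (d = 5-30%), 13% under the pool and a quarter under the open-arm draw.

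**An open list.** Suppose 39 dyads are randomised 13/13/13 and d = 20%. Expected completers are 13 x 0.8 = 10.4 per arm, with SD √(13 x 0.2 x 0.8) = 1.4. The total is 39 x 0.8 = 31.2, with SD √(39 x 0.2 x 0.8) = 2.5. No assignment depends on a vacancy.

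**The case against.** The strongest reply is that the plan states no faulty rule. The stop by arm and the 30 full-duration cases are in separate sentences, and the second is a total. Researchers only recruit replacements, while randomisation stays with the statistical team. Carrying on the list until every arm has at least 10 would also fit the first sentence. This stands as far as it goes: same-arm substitution is an inference. But a list kept open until each arm has 10 completers will usually pass 30, so it sits badly with 30 cases at 10 per arm. Meeting both targets requires closing arms.

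A reader might infer three stronger things that the documents do not support:

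- *That the non-random share equals the drop-out rate.* That rate is the share of replacements. It is the forced share only under direct same-arm substitution, which is nowhere stated.
- *That allocation was not concealed.* Concealment is undescribed, not shown to be absent. The statistical team could conceal assignments from recruiters who do not know the arm counts, and the detailed protocol may describe this.
- *That the affected dyads concentrate in the active arms.* The active programmes ask more of caregivers, but controls receive only a pamphlet and are offered a kit after follow-up, which could also prompt withdrawal. At 30% active and 10% control drop-out, replacements would be 2 x 10(0.3/0.7) = 8.6 active and 10(0.1/0.9) = 1.1 control, or 88% active. That percentage comes entirely from the assumed split.

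It is also fair to say that this is an exploratory study without full power, that the application is marked closed, and that the Statistical Analysis section is in the past tense. Those facts limit what rewording can achieve now. They do not remove the need to report how replacements were assigned.

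**Conclusion.** The concern holds in a limited form, as something the sponsor should address. The fixed number per arm, combined with replacement of drop-outs and no stated allocation rule, makes some late assignments depend on the vacancy and potentially foreseeable. It is more than a missing detail, because the stated quota itself creates the problem. The forced share is roughly 3-10% of assignments under random refilling, and up to the drop-out rate under direct refilling. These figures assume equal, independent drop-out of 5-30%; the plan gives no rate. Foreseeability also requires that screening staff know the arm counts, which the described roles make plausible but do not prove. Neither the direction nor the size of any resulting bias can be derived from the documents. If the detailed protocol contains an allocation and concealment rule for replacements, citing it may settle the point.

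**What to change.** In Research Procedures, state that every additional dyad takes the next assignment on the statistical team's concealed 1:1:1 list, whichever arm the drop-out came from. Define the recruitment stop as a total number randomised, not as 10 completers per group. Say who holds the list and how assignments are released. Vary the block sizes and do not disclose them: in a fixed block of three, the last assignment is known to anyone who saw the first two. Check the chosen total against the application's maximum of 56 human subjects, and say whether that counts dyads or individuals. Counted as individuals in dyads, it allows 56/2 = 28 dyads, fewer than 30.

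For dyads already enrolled, report how each replacement was assigned. Flag any placed to fill a vacancy and repeat the arm comparisons without them as a sensitivity analysis. With the application closed, this is the part that can still be acted on.

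The cost is a few sentences and no new procedures. The price is somewhat unequal completer numbers and no guarantee of exactly 30. Insisting on at least 10 completers in every arm from an open list costs more. In simulation with blocks of three and 20% drop-out, that took 41.3 dyads on average, gave 33.0 completers, and ended on exactly 30 in 13% of runs.

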Summary statistics will be tabulated by treatment arm for the baseline, week 4, and week 8 outcome measures of VABS, NPI, and protocol adherence based on behavior journals. The change from baseline to week 4 and follow-up will be calculated for each patient. Descriptive statistics will be examined to see whether levels of each assessment at baseline are normally distributed. If they are, then the mean changes will be compared in each treatment group with the standard of care group by analysis of variance (ANOVA). If they are not normal, then consideration will be given to data transformation.

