For this study, the following step-by-step sequence will be used. Recruitment will occur via discussion with SBCOA medical team (MD/APRN/PA) and [name] of appropriate referrals of heightened cognitive impairment with behavioral disturbance. Additionally, SBCOA records will be reviewed for all eligible cohort participants. These participants will be contacted via SBCOA recruitment team with calling, mailing, and/or emailing eligible participants with an invitation to participate in the current study. Following agreement to participate, SBCoA staff and researcher will coordinate with the participant a date and time for Visit 1 to be completed via a virtual telemedicine platform. All visits within this study will be scheduled at times convenient for the participants using telemedicine Zoom video conferencing. Videos will be recorded and saved on private and secure server hosted by Sanders-Brown Center on Aging Data Management Team.

During the screening visit, a research assistant or PI will review and obtain consent as described above, talk with the LAR and caregiver to determine eligibility status, and record medications. The PI will complete a UKADC or KNI chart review of medical conditions, medications, and symptoms from the prior 24 months if available. Records will be assessed for most recent vital signs (systolic and diastolic blood pressure, pulse, temperature, and respiration), known allergens, chronic medical conditions, recent medical changes, and medications. The PI (OT) or UKADC medical staff (MD/APRN/PA) will conduct a physical and neurological examine via Telemedicine. The physical examination will include skin, head/ears/eyes/nose/throat (HEENT), oral/teeth/gums (history of dental problems/dentures), sensory function, gait/walking ability, and musculoskeletal range of motion of upper extremities. All complete physical and neurological examination data will be entered on the appropriate CRF. Neurological assessment will include of cranial nerves, strength, coordination, symmetry of movements, and movement speed. Verbal assessment of patients' sensory function (including hypersensitivity) with caregiver will occur at the screening. Significant abnormalities consistent with disease processes will be documented.

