Visit 9 will conclude the intervention window at the end of week 4. The PI, occupational therapist, research assistant will record adverse events, concurrent medication, Actigraph, and weekly behavior journals/compliance. The research assistant will conduct the NPI, COPM, VABS with the caregiver and the MOCA with the person with dementia. A member of the SBCoA medical team will conduct a physical and neurological exam. Due to the length of assessments within Visit 7, this session may be split and completed in more than one Zoom conference. The Zarit Caregiver Burden Scale will be emailed or mailed to the caregiver with prepaid envelop for return.

A four-week follow up will be conducted at Visit 10 whereby the research assistant will conduct the NPI, COPM, VABS with the caregiver, and the MOCA with the person with dementia. A member of the SBCoA medical team will conduct a physical and neurological exam. The Zarit Caregiver Burden Scale will be emailed or mailed to the caregiver with prepaid envelop for return.

Schedule of events can be found in attached detailed protocol.

A list of potential items sent in sensory kit is attached here.

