#### Behavioral Journal

Behavior journals will be kept by caregivers daily during the 4-week intervention. Behavior journals will be used to measure adherence to the treatment protocol using a daily tracking log, prompt care partner reflection of each week's intervention use, and monitor behavioral changes throughout the intervention. Journals will be reviewed weekly with study personnel and returned to investigator at intervention completion on week 4 visit. Analysis will include quantitative

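### The journal-based adherence summary can leave out dyads who stop early, because journals come back at week 4 and dropouts are replaced

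*Combined protocol and SAP*

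**What the plan says.** Objective 1 is feasibility, including adherence to the intervention. Under Primary measures, adherence is measured with the behavioral journal and an intervention adherence log, and weekly check-ins review it. The same list lets the PI remove a participant found to be noncompliant.

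The visit text in Research Procedures separates what is recorded from what is reviewed:

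- Visits 4-8, recorded: "The PI, occupational therapist, or research assistant will record concurrent medication, and adverse events".
- Visits 4-8, reviewed: "the interviewer will review behaviors observed by the caregiver, the behavior journal, compliance and acceptance of the intervention".
- Visit 9, end of week 4: "The PI, occupational therapist, research assistant will record adverse events, concurrent medication, Actigraph, and weekly behavior journals/compliance".

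The Behavioral Journal section says: "Journals will be reviewed weekly with study personnel and returned to investigator at intervention completion on week 4 visit". Research Materials, Records and Privacy makes the journal the one item that is not electronic; paper copies are scanned later. Visits are remote: "All visits within this study will be scheduled at times convenient for the participants using telemedicine Zoom video conferencing".

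Research Procedures also says that dropouts and early terminations are replaced, so that the study ends with 30 cases of full duration.

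The adherence result is then defined in more than one way. Data Analysis sets a 75% threshold for the per-protocol analysis, determined from weekly visits and journals, and also tabulates "protocol adherence based on behavior journals" by arm. The Statistical Analysis section defines the primary endpoint as completing at least 75% of the video sessions, compared among arms by chi-square. Its modified intention-to-treat rule is stated for secondary and exploratory endpoints only.

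**The concern.** Loss of a journal is unlikely to be independent of adherence. A dyad that is struggling with the kit is more likely to stop, and one judged noncompliant may be removed. Either can happen before the journal is due back. The dyad's place then goes to a replacement who is expected to finish. If the journal is the data source and full-duration cases are the set, the summary describes adherence among those who stayed. In a feasibility study that is the wrong group: early stopping is itself a feasibility finding, and leaving it out makes the two active protocols look easier to deliver than they were.

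Session attendance does not fill the gap. A caregiver can attend every call and seldom use the kit. The journal and log are the only day-level record of intervention delivered that the documents describe.

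**Working it through.** **1. Is there a figure to reproduce?** Only the sample size: 3 arms × 10 = 30, which agrees with Data Analysis. The documents give no dropout rate, no expected adherence, and no power calculation. The rest is a reading of the text plus an illustration.

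**2. The path of an early stopper through the plan**

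| Step | What the documents provide |
|---|---|
| Weekly calls before stopping | Journal and compliance reviewed; no entry of an adherence value stated |
| Visit 9 recording of journals and compliance | Not reached |
| Return of the paper journal | Tied to the week 4 visit; no return route described, whereas prepaid return is described for the Actigraph, the Adult Sensory Profile and the Zarit scale |
| Termination visit (Data and Safety Monitoring Plan) | Required after exit for an adverse event; journal collection not mentioned |
| Place in the sample | Filled by a replacement |
| Rule for scoring adherence | None found |

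Same-day upload to REDCap runs from acquisition of the data, which for the paper journal is week 4.

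**3. Can an early stopper count as adherent?** The intervention lasts 4 weeks, or 28 days. Perfect use up to stopping gives 7/28 = 25% after one week, 14/28 = 50% after two and 21/28 = 75% after three. A dyad that stops before the end of week 3 cannot reach 75% of planned days, so counting it as non-adherent is reasonable. One that stops later might still qualify.

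**4. Size, by assumption.** Let a be the number of adherent completers among 10 in an arm, and k the number of early stoppers who were replaced and count as non-adherent.

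- Completers only: a/10
- All randomised: a/(10 + k)

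| a | Completers only | k = 1 | k = 2 | k = 3 |
|---|---|---|---|---|
| 6 | 60% | 54.5% | 50.0% | 46.2% |
| 7 | 70% | 63.6% | 58.3% | 53.8% |
| 8 | 80% | 72.7% | 66.7% | 61.5% |
| 9 | 90% | 81.8% | 75.0% | 69.2% |

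For a = 8 and k = 2: 8/(10 + 2) = 66.7%, so the completers-only rate is 13.3 points too high. Over a = 6 to 9, the overstatement is about 5 to 8 points for k = 1, 10 to 15 for k = 2 and 14 to 21 for k = 3.

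**5. The primary endpoint.** Attendance at video sessions can be scored without a journal, so late return does not touch it. Its denominator is a separate matter. Suppose 8 of 10 completers meet the threshold in each arm and 0, 2 and 4 dyads were replaced. Completers show 80% in all three arms; all randomised dyads show 8/10 = 80%, 8/12 = 67% and 8/14 = 57%. The chi-square is 1.37 on 2 degrees of freedom (p = 0.50). At this size it is the described rates that change, not the test result.

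**The case against.** The strongest reply is that weekly capture is plainly intended. Study Design plans weekly monitoring of adherence, Primary measures names an adherence log beside the journal, and Data Analysis takes the 75% threshold from weekly visits as well as journals. Visits are video-recorded, and interviews are to be transcribed and kept on REDCap. The schedule of events is in a detailed protocol that is attached but not shown, as is the journal form, and the Behavioral Journal text breaks off where the analysis begins. Any of these may contain a weekly recording step.

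Much of this stands. A reader might infer that a dyad who stops early has no day-level adherence record at all. The documents do not support that: information may exist in the log, the recordings or an unseen form. What remains is that the visible visit procedure has no step turning the weekly review into an adherence value, one planned summary rests on journals alone, and nothing says how stopped or replaced dyads count.

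A reader might also infer that the late journal biases the primary result. It does not, because session completion is known to staff.

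It is also fair to say that counting days after stopping as not delivered is a scoring choice. It is the natural one when the question is whether the protocol can be delivered for its planned duration.

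**Conclusion.** The concern holds for the journal-based adherence summary. Followed as written, the plan tilts that summary towards completers through three features together: paper journals due at week 4, a recording step stated only at Visit 9, and removal and replacement until there are 30 full-duration cases. Replacement is the strongest of the three.

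For the primary endpoint the point is narrower. Late journal return has no effect, but no analysis set is named, so replaced dyads could be lost from the denominator.

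With 8 of 10 completers adherent, 1, 2 or 3 replaced early stoppers in an arm would move the rate from 80% to 73%, 67% or 62%. This assumes that the stoppers are non-adherent and would otherwise be left out. It shows what the gap could do, not that it occurred. Confidence is moderate because the detailed protocol and journal form cannot be seen.

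**What to change.** 1. In the text for the weekly visits, add that the interviewer enters that week's daily adherence log, day by day, into REDCap while going through it with the caregiver. Use the returned paper journal as a check.
2. Report adherence for every randomised active-arm dyad, including those removed or replaced, counting intervention days after stopping as not delivered. A completers-only figure can stand beside it if labelled as such.
3. State that the primary endpoint uses all randomised dyads.
4. Reconcile the adherence definition in Data Analysis (weekly visits and journals) with the one in Statistical Analysis (video sessions), saying which is primary. Give the number of sessions behind the 75%. Visits 4-8 are five visits at weekly intervals inside a 4-week window that Visit 9 closes, so the threshold could mean 3 of 4, 4 of 5 or 5 of 6.

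The Statistical Analysis section is written in the past tense. If data collection is over, report by arm how many dyads stopped or were replaced, how many journals were recovered, and how those dyads were counted.

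The cost is one REDCap form and a few minutes in calls that already take place. Reported adherence may be lower.
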